## 9. SCREENING

9.1 Will you be screening participants for eligibility? *Note that If you are using inclusion or exclusion criteria, you will be “screening” individuals in order to determine who is eligible.*

Yes

No (*skip to next section*)

9.2 Explain what your screening criteria will be and how you will conduct the screening process.

When new users access certain types of articles, a dialog box will appear asking them if they are interested in participating in a study aimed at helping The Mighty understand the impact of the articles posted by other users on its platform and asking if they would like more information. Prospective participants who respond “yes” will be prompted to fill out a brief screening survey to indicate their age and history of suicidal thoughts and behaviors.

9.3 Do you plan to destroy the data from people who participate in the screening process and do not qualify to be in the study as soon as the screening process is over?

Yes

No (*see below*)

***If “No” explain why you will keep the data collected in the screening process for people who are not eligible to participate in this study.***

We plan to destroy data from participants who participate in the screening process and do not qualify for the study after the enrollment has ended. However, we would like to retain screening data from the participants who do not qualify for the study to ensure that they do not attempt to re-enroll and provide false screening information at a later time.

## 10. INFORMED CONSENT PROCESS

*If you plan on having more than one consent process (such as signed, written consent for one population and use of an online “click” consent script for another population), please explain which variations of the study will use which types of consent process with each of these questions.*

### ADULT PARTICIPANTS

*If you will not include adults in your study, please skip this section.*

10.1 Will you be obtaining informed consent or an agreement to participate (for Exempt studies) from participants that take part in your study?

Yes, I will be obtaining informed consent or an agreement to participate.  
 No, I will not be obtaining consent or an agreement to participate (**skip to next section after answering below**)

*If you will not be obtaining consent or an agreement to participate, please explain:*

- **why this research involves no more than minimal risk to participants and**
- **why it would be impracticable to carry out the research with consent or an agreement to participate**

Participants will consent to their data from their user profile in TheMighty to be linked with their survey responses.

10.2 Will the consenting or an agreement to participate process involve obtaining a signature?

Yes  
 No (**see below**)

*If a signature is not obtained, explain why:*

The proposed study will be conducted online, so a physical signature is not feasible. An electronic consent form will be used instead.

10.3 Where will the consent or an agreement to participate process take place?

In-person  
 Online  
 Over the telephone  
 Other (**see below**)

*If other, please describe:*

10.4 Who will obtain consent or an agreement to participate from participants? *Will the Principal Investigator, other members of the Harvard University research team, collaborating researchers from other institutions, or another third party (such as a survey firm) obtain consent?*

The consent form will be an automatic pop-up on TheMighty's website, which will be managed by team members at TheMighty.

10.5 Describe the process that will be used to obtain consent or an agreement to participate.

Consent will be obtained digitally, by simply having the participant click "agree" before they can continue. There will be an option for users to print or download the consent form for their records.

10.6 Describe how you will assess comprehension of the research and what it means to participate, including understanding of the voluntary nature of participating.

Research subjects can decline participation. We will include language that explicitly states that participation is entirely voluntary, and that refusal to participate will not limit their access to the resources on the website in any way

## CHILDREN PARTICIPANTS

*If you will not include children in your study, please skip this section.*

*If you are including children in your research study, know that consenting or requesting an agreement to participate from a child is comprised of two parts: child assent and parent permission.*

10.7 Will you be obtaining assent or an agreement to participate (for Exempt studies) from child participants that take part in your study?

- Yes, I will be obtaining assent or an agreement to participate.
- No, I will not be obtaining assent or an agreement to participate (**skip to next section after answering below**)

*If you will not be obtaining assent or an agreement to participate, please explain:*

- **Why this research involves no more than minimal risk to participants and**
- **Why it would be impracticable to carry out the research with assent or an agreement to participate:**

10.8 Will the assenting or an agreement to participate process involve obtaining a signature?

- Yes
- No (**see below**)

*If a signature is not obtained, explain why:*

10.9 Where will the assent or an agreement to participate process take place?

- In-person
- Online
- Over the telephone
- Other (*see below*)

*If other, please describe:*

10.10 Who will obtain assent or an agreement to participate from child participants? *Will the Principal Investigator, other members of the Harvard University research team, collaborating researchers from other institutions, or another third party (such as a survey firm) obtain the assent?*

10.11 Describe the process that will be used to obtain assent or an agreement to participate from children.

10.12 Describe how you will assess comprehension of the research and what it means to participate, including understanding of the voluntary nature of participating.

## PARENT PERMISSION

*If you will not be including children in your research, please skip this section.*

10.13 Will you be obtaining parent permission or an agreement to participate (for Exempt studies) from parents whose child takes part in your study?

- Yes, I will be obtaining parent permission or an agreement to participate.
- No, I will not be obtaining parent permission or an agreement to participate (*skip to next section after answering below*)

*If you will not be obtaining parent permission or an agreement to participate, please explain:*

- *Why this research involves no more than minimal risk to participants and*
- *Why it would be impracticable to carry out the research with parent permission or an agreement to participate:*

10.14 Will the parent permission or an agreement to participate process involve obtaining a signature?

- Yes

No (see below)

**If a signature is not obtained, explain why:**

10.15 Where will the parent permission or an agreement to participate process take place?

- In-person
- Online
- Over the telephone
- Other (*see below*)

**If other, please describe:**

10.16 Who will obtain parent permission or an agreement to participate from the parents? *Will the Principal Investigator, other members of the Harvard University research team, collaborating researchers from other institutions, or another third party (such as a survey firm) obtain the permission?*

10.17 Describe the process that will be used to obtain parent permission or an agreement to participate from parents.

10.18 Describe how you will assess comprehension of the research and what it means to participate, including understanding of the voluntary nature of participating.

## OTHER TYPES OF PARTICIPANTS

*If this section is not applicable, skip to next section.*

10.19 If you will be including **Wards of the State**, explain how consent of legal guardian(s) of ward(s) will be obtained. How will you ensure that the appropriate person granted permission for each ward to participate?

10.20 If you will be obtaining consent from special populations such as **non-English speaking participants, illiterate participants, or adults not competent to consent**, please explain how you will obtain consent from those individuals.

10.21 Describe how you will assess comprehension of the research and what it means to participate, including understanding of the voluntary nature of participating.

***Please be sure to attach copies of all informed consent/parent permission/assent materials to the “Local Site Documents” section in the ESTR SmartForm.***

## 11. PARTICIPANT COMPENSATION AND FINANCIAL OBLIGATION

11.1 Will your study offer any compensation/incentive to participants (including cash, gift cards, course credit, etc.)? Please refer to the [Harvard University Financial Policy on Human Subject Payments](#).

Yes  
 No (*skip to #11.6*)

11.2 What type of compensation will you provide to participants?

Cash  
 Check  
 Gift Card/Gift Certificate  
 Course Credit  
 Lottery/Raffle  
 Other (*see below*)

***If you chose “Other” please specify:***

11.3 What amount will the compensation be worth?

Compensation for the study will include entry into a raffle to win one of two \$250 checks. One check will be allocated to participants in the AT condition and the other to those in the Control condition.

11.4 Describe which participants will receive compensation and when the compensation will be given.

Participants in each condition (AT and Control) will be assigned one numbered token for each completed survey during the entire study period. Participants will need to complete 75% of the daily surveys in order to qualify for a raffle, in which one token from the each group will be randomly selected at the end of study (week 4 for AT condition; week 8 for the Control condition). The two owners of those tokens will be asked for their physical mailing address so we can send them each a \$250 check. If a winning participant is not able to provide a mailing address, they will not be eligible to win the \$250 check.

11.5 Will you provide partial compensation for participants who do not complete all the study procedures?

Yes (see below)

No

*If "Yes" please explain how partial compensation will be managed:*

**HRP-316 WORKSHEET: PAYMENT which may be found in the ESTR library provides an overview of items pertaining to payment that may be helpful to the study team.**

11.6 Will participants incur any financial costs by taking part in this study?

Yes (see below)

No

*If "Yes" please explain.*

## 12. DATA SECURITY AND MANAGEMENT

12.1 Describe the identifiability of the data when first obtained/collected:

Will not contain any direct or indirect identifiers (Anonymous)

Will not be directly identifiable but there will be a code held by the data source that links to the identities (Coded) – *i.e., if receiving data from another site*

Will contain direct identifiers (Identifiable)

12.2 Describe the identifiability of the data when stored:

Will be directly labeled with personal identifying information (Identifiable)

Will be labeled with a code that the research team can link to personal identifying information (Coded)

Will not be labeled with any personal identifying information, nor with a code that the research team can link to personal identifying information (Anonymous or De-identified)

Other - explain here:

12.3 Which category of information best describes the data according to the [Harvard Research Data Security Policy](#)? **Please know that it is the researcher's responsibility to ensure compliance with the Harvard University Data Security Policy at all times.**

LEVEL 1 - Data that is publicly available or not identifiable. Examples:

- Research data that has been de-identified in accordance with applicable rules;
- Published research data; published information about the University;
- Course catalogs;

- Directory information about students who have not requested a FERPA block;
- Faculty and staff directory information.

LEVEL 2 - Information the University has chosen to keep confidential but the disclosure of which would not cause material harm. Examples:

- Research data that is identifiable but is not considered sensitive;
- Patent applications and work papers, drafts of research papers;
- Building plans and information about the University physical plant.

LEVEL 3 - Information that could cause risk of material harm to individuals or the University if disclosed. Examples:

- Information protected by the Family Educational Rights and Privacy Act (FERPA) to the extent it is not covered under Level 4 including non-directory student information and directory information about students who have requested a FERPA block;
- HUIDs associated with names or any other information that could identify individuals;
- Harvard personnel records (employees may discuss terms and conditions of employment with each other and third parties);
- Institutional financial records;
- Individual donor information;
- Other personal information protected under state, federal and foreign privacy laws not classified as Level 4 or 5.

LEVEL 4 - Information that would likely cause serious harm to individuals or the University if disclosed. Examples:

- High Risk Confidential Information (HRCI) and research information classified as Level 4 by an IRB;
- Personally identifiable financial or medical information;
- Information commonly used to establish identity that is protected by state, federal, or foreign privacy laws and regulations;
- Individually identifiable genetic information that is not Level 5;
- National security information (subject to specific government requirements);
- Passwords and Harvard PINs that can be used to access confidential information.

LEVEL 5 - Information that would cause severe harm to individuals or the University if disclosed. Examples:

- Research information classified as Level 5 by an IRB or otherwise required to be stored or processed in a high security environment and on a computer not connected to the Harvard data networks;
- Certain individually identifiable medical records and genetic information, categorized as extremely sensitive.

12.4 In what format will the research data be **collected**?

Paper  
 Electronic  
 Other – **(see below)**

**If "Other" please specify:**

12.5 In what format will the research data be **stored**?

Paper  
 Electronic  
 Other – **(see below)**

If "Other" please specify:

12.6 Explain **where** the research data will be stored while the study is active (e.g., personal laptop, thumb drive, departmental computer server, office file cabinet, etc.).

The data will be initially stored on encrypted servers by TheMighty and will be then transferred to Harvard University computer servers.

12.7 Will the data be managed by Harvard researchers either remotely or housed at Harvard (e.g., physically or Harvard Cloud Storage)?

Yes

No

12.8 Do you anticipate that the research data will be transferred or transported from your possession to another at any time?

Yes

No (*skip to question #12.10*)

12.9 Explain what methods you will use to transfer/transport the data and how you will minimize the risks of a data breach during the transmission process.

12.10 Will data be transferred from the EEA\* to Harvard or another non-EEA location?

Yes

No

**\* The EEA includes the 28 states of the European Union and four additional countries: Iceland, Liechtenstein, Norway and Switzerland.**

12.11 Will (or has) a Certificate of Confidentiality (CoC) be (been) obtained for this study? *If your study meets the definition of a clinical trial according to the NIH, a CoC will be automatically issued with your funding.*

Yes

No

12.12 What will happen to the data at the conclusion of the study? (check all that apply)

Direct identifiers\* and/or the key to the codes will be destroyed upon completion of the research (all data will be stripped of identifying information and/or the key to codes destroyed, identifiable paper documents shredded, identifiable electronic files purged, Identifiable electronic media securely erased).

Retained for study record keeping purposes per institutional policy.

Retained by the investigator for future research use.

Retained for future research use (create repository/bank).

Restricted use data will be destroyed or will be returned to the source.

- No direct or indirect identifiers\* are being collected. This anonymous data will be retained at the discretion of the investigator.
- This research is a clinical trial conducted under FDA regulations. Direct identifiers\* and/or the key to the codes will be destroyed as directed by the sponsor (IND/IDE holder) in accordance with FDA regulations.
- Other – **(see below)**

*\* Direct identifiers. These are variables that point explicitly to particular individuals or units. Examples include: names, addresses, including ZIP and other postal codes, telephone numbers, including area codes, Social Security numbers, other linkable numbers such as driver's license numbers, certification numbers, etc.*

*Indirect identifiers. These are variables that can be problematic as they may be used together or in conjunction with other information to identify individual respondents. Examples include: detailed geographic information (e.g., state, county, province, or census tract of residence), organizations to which the respondent belongs, educational institutions (from which the respondent graduated and year of graduation), detailed occupational titles, place where respondent grew up, exact dates of events (birth, death, marriage, divorce), detailed income, offices or posts held by respondent.*

**If "Other" please specify:**

### 13. SHARING DATA WITH OTHERS

13.1 Will the data be released to anyone who is not on the Harvard University Area research team?

- Yes
- No **(skip to question #13.4)**

13.2 Other than the Harvard University Area research team, who will have access to the data?

- Colleagues/Collaborators at other institutions
- Transcribers/coders hired by the research team
- Sponsor/Funding Agency
- Other **(see below)**

**If "Other" please specify:**

13.3 How will the data be shared/disclosed beyond the Harvard University Area research team?

- Without any identifiers
- Coded
- With Identifiers

13.4 Will you be sharing research findings with study participants?

- Yes **(see below)**
- No

**If "Yes" please describe which findings will be shared, when they will be shared, and how they will be shared with participants (in-person, over the telephone, etc.):**

13.5 Does the study include establishing a repository for sharing data or specimens with other researchers?

Yes (*If so, please know that a separate IRB submission will be needed if a data or specimen repository will be created*)  
 No

#### GENOMIC DATA SHARING

13.6 Will you be submitting data to a national data repository (dbGaP, GEO, etc.) or other type of repository for broad sharing of data?

Yes  
 No (*skip to next section*)

13.7 Will you require a Genomic Data Sharing (GDS) Institutional Certification per NIH GDS policy?

Yes  
 No

13.8 Include a description of all fields to be submitted to the repository:

13.9 Describe the plan for de-identifying data for inclusion in the repository, including how the key linking the identity of participants will be maintained and who will have access:

*If data will be prospectively collected, specific elements are required to be included in the informed consent form that you will be using in this study. Please see the [NIH guidance document](#).*

*If data that will be submitted have already been collected under another IRB or other collection protocol, please be sure to attach a copy of the IRB approval and approved consent form(s) used to collect the underlying data/specimens to the "Local Site Documents" section in the ESTR SmartForm.*

Title of study: Digital Narrative Bibliotherapy as a Scalable Intervention for Suicidal Thoughts

Document date: November 20, 2020

Document type: Statistical Analysis Plan

STATISTICAL ANALYSIS PLAN

We used an intent-to-treat design for all analyses, which were performed in RStudio.

Hypothesis 1: We predicted that the narrative bibliotherapy intervention would lead to lower ratings of the desire to die among participants assigned to the Treatment group, relative to those assigned to the Control group.

- **Analysis:** We used a mixed effects model as implemented in the *lme4* package to test whether participants in the Treatment group reported lower desire to die across the 14-day study period. This model included group (Treatment vs. Control) and day of the survey fixed effects. We also controlled for the effects of previous history of suicidal thoughts by including this measure as participant-level fixed effects.

Hypothesis 2: We predicted that the effect of the treatment would persist two weeks after the conclusion of the trial.

- **Analysis:** We used a *t*-test to examine group differences (Treatment vs. Control) in desire to die at the two-week follow up point.

Hypothesis 3: We predicted that participants who completed more days of the trial would report lower desire to die if they were assigned to the Treatment group (i.e. dose response effect).

- **Analysis:** We used a mixed effects model as implemented in the *lme4* package to tested the effect of the number of days of participation on participants' desire to die across the 14-day study period. This model included group and days of participation as participant-level fixed effects.

Hypothesis 4: We predicted that reductions in the desire to die resulting from reading suicide narratives to die would be attributable to increased feelings of optimism and connectedness.

- **Analysis:** We used mediation analysis as implemented in the *lavaan* package to examine the indirect effect of connectedness and optimism on the association between group assignment and desire to die.

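### The SAP tests four hypotheses with no stated significance level, primary hypothesis or testing order, so persistence at follow-up could be claimed when Hypothesis 1 shows no effect

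*SAP*

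**What the plan says.** The SAP opens with one general statement: "We used an intent-to-treat design for all analyses, which were performed in RStudio". It then lists four predictions, each followed by its own analysis.

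- **Hypothesis 1**, the group difference during treatment. A mixed model is used to "test whether participants in the Treatment group reported lower desire to die across the 14-day study period".
- **Hypothesis 2**, duration: "We predicted that the effect of the treatment would persist two weeks after the conclusion of the trial". A t-test is used to "examine group differences (Treatment vs. Control) in desire to die at the two-week follow up point".
- **Hypothesis 3**, dose response. A second mixed model is fitted: "This model included group and days of participation as participant-level fixed effects".
- **Hypothesis 4**, mechanism. Reductions in the desire to die "would be attributable to increased feelings of optimism and connectedness". A mediation analysis is used to "examine the indirect effect of connectedness and optimism on the association between group assignment and desire to die".

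Neither document gives a significance level, says whether tests are one- or two-sided, names a primary hypothesis or outcome, or sets a testing order or multiplicity rule. Protocol section 5.2 lists four questionnaire constructs without ranking them.

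The protocol does order the questions in prose. Section 4.2 asks first whether the curriculum lowers suicidal thoughts and behaviors and then, on condition that it does, for how long. Section 5.1 (Part 2) describes the two-week follow-up as a check on whether the effect of reading is sustained.

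**The concern.** Hypothesis 2 is a statement about an effect already shown. Its test, however, is an ordinary comparison of the two groups at one later time, and nothing in the SAP makes it depend on Hypothesis 1. If the mixed model shows no difference over the 14 days and the follow-up t-test gives a small p-value, the SAP as written lets the result be reported as confirmation that the effect lasted.

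The wider problem is that each of the four predictions stands on its own, so any one success could be presented as support for the intervention. Without a primary hypothesis and a significance level, a reader of the results cannot tell which finding carries the trial's conclusion or what its error rate is. The protocol hopes that clinicians will refer patients to the intervention if it succeeds (section 4.2), so this matters.

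**Working it through.** **Plan's own figure.** There is none to reproduce: the documents state no significance level, power or familywise error rate.

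**Inputs.**
- Number of tests: four (SAP, Hypotheses 1 to 4), or five if optimism and connectedness are tested separately. The SAP does not say which.
- Level per test: not stated. Assumed two-sided 0.05, with 0.01 and 0.10 as a range.
- Correlation between test statistics: not stated. Hypotheses 1, 2 and 4 share the outcome and the randomised groups, so positive correlation is likely. Range 0 to 0.9.
- Setting: no true effect anywhere (the global null).

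**Step 1. Independent tests.** The chance of at least one false rejection is 1 − (1 − α)^k.
- Four tests: 1 − 0.95^4 = 18.5%. The upper bound under any correlation is 4 × 0.05 = 20%.
- Five tests: 1 − 0.95^5 = 22.6%.
- Four tests at α = 0.01: 1 − 0.99^4 = 3.9%. At α = 0.10: 1 − 0.90^4 = 34.4%.

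**Step 2. Correlated tests.** These come from 1,000,000 simulated sets of four normal statistics at two-sided 0.05.

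| Correlation | All four equally correlated | Only Hypotheses 1, 2 and 4 correlated |
|---|---|---|
| 0.5 | 15.6% | 16.9% |
| 0.7 | 13.0% | 15.5% |
| 0.9 | 9.4% | 13.0% |

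**Step 3. False claims of benefit only.** Half of the two-sided rejections of a single test favour control. Counting the predicted direction alone, four independent tests give 1 − 0.975^4 = 9.6%. Simulation gives 7.7% at an equal correlation of 0.5 and 4.7% at 0.9. A single two-sided 5% test gives 2.5% in that direction.

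**Step 4. Hypotheses 1 and 2 alone.**
- At least one false rejection: 1 − 0.95^2 = 9.75% if independent; by simulation 9.0% at correlation 0.5 and 8.3% at 0.7.
- Hypothesis 2 significant while Hypothesis 1 is not: 0.95 × 0.05 = 4.75% if independent; by simulation 4.1% at 0.5 and 3.3% at 0.7. By symmetry half of this favours treatment: about 2.4%, 2.0% and 1.7%.

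**Step 5. The same two hypotheses in a fixed sequence.** If Hypothesis 1 has no true effect, any false claim needs a false rejection of Hypothesis 1 first, so the chance is 5%. If Hypothesis 1 is true and Hypothesis 2 is not, the only possible error is in the second test, at most 5%. The pair is held at 5% in either case.

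**Step 6. Do all four tests really have size 5%?** Not necessarily. If mediation is judged by requiring both paths to be significant and neither path is real, its size is about 0.05 × 0.05 = 0.25%. The four-test figure is then 1 − 0.95^3 × 0.9975 = 14.5% if independent.

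**The case against.** The strongest reply is that the order is already there. Section 4.2 of the protocol makes duration conditional on an effect, and the wording of Hypotheses 2 and 4 presupposes one. That is right about intent, and it is why the fix should be uncontroversial. But the SAP does not turn the intent into a testing rule, and an order left to inference does not restrict what can be reported.

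Other objections limit how far the point can be taken, and they stand.

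- **A reader might infer that the plan has a false-positive rate of some 16–19%.** The documents do not support that as a property of the plan. It needs an assumed level, four tests of true size 5%, and correlation no higher than about 0.5. It also counts rejections in which treatment looks worse. Moreover, Hypothesis 3 is not a clean treatment test: its model has no group-by-days term, and a coefficient for days of participation is a non-randomised association.
- **A reader might set 18.5% beside the 5% of a fixed sequence.** That compares four tests with two. The like-for-like figure for Hypotheses 1 and 2 is 9.75% if independent.
- **A reader might infer that mediation can never be discussed unless Hypothesis 1 is significant, or that the results would contradict one another.** A delayed difference, or an indirect effect without a significant total effect, is coherent. Requiring a significant total effect is a debatable choice. It is enough not to treat Hypothesis 4 as confirmatory evidence of efficacy.
- **A reader might infer that one-sided tests are planned, or that protocol section 6.1 rules them out.** The SAP specifies no one-sided test, and directional predictions are commonly tested two-sided. Section 6.1 concerns individual readers who may worsen although the articles help as a group; it does not settle sidedness. The gap is simply that sidedness is not stated.

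**Conclusion.** The concern holds on structure. Four predictions are tested with no stated level, primary hypothesis or order, and the SAP omits the protocol's own condition that duration is asked about only if there is an effect. As written, the follow-up t-test could be reported as persistence after Hypothesis 1 shows nothing.

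The size is conditional. With each test at two-sided 5% and no true effect anywhere, the chance of at least one false rejection is 18.5% for four independent tests, 15.6% at correlation 0.5, 9.4% at 0.9, and 22.6% for five independent tests. Restricted to false claims of benefit, the four-test figure is about 8–10% for correlations from 0 to 0.5. For Hypotheses 1 and 2, where the missing condition bites, it is 9.75% if independent and about 8.3% at correlation 0.7, against 5% with a fixed sequence. The level, the correlations and the handling of the two mediators are assumptions.

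The SAP is written in the past tense. A reader might infer that the analyses had already been run when it was written; the documents do not say so. This affects how a testing order added now must be described, not whether one is needed.

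**What to change.** Add to the SAP:

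1. Hypothesis 1 is the primary hypothesis, tested at two-sided 5%.
2. Hypothesis 2 is tested at two-sided 5% only if Hypothesis 1 is significant. Otherwise the follow-up difference is reported descriptively, with its confidence interval and no claim of persistence.
3. Hypotheses 3 and 4 are exploratory, reported with confidence intervals, and not presented as confirmatory evidence of efficacy.
4. If any outcome data had been seen before this order was set, it is reported as post hoc. It then still restrains the claims but does not make them confirmatory.

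The cost is a few sentences. Hypothesis 1 keeps its full 5% and loses no power. By contrast, a Bonferroni split over all four hypotheses would test Hypothesis 1 at 0.05 / 4 = 0.0125. The real loss is that a follow-up difference without a significant Hypothesis 1, including a genuinely delayed effect, can be described but not claimed.
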